1.2 Secondary Objective

- To assess overall pain control and management for patients on celecoxib compared to placebo.

Secondary Endpoints:

- Subjective pain scores on the visual analog scale of pain intensity averaged over a week at rest, with a swallow, and with a cough.
- Patient satisfaction with pain control questionnaire.
- Narcotic consumption in daily total morphine equivalents averaged over a week.

- To assess functional outcomes for patients on celecoxib compared to placebo

Secondary Endpoints: Current activity level and swallowing capabilities, including food and liquid variety and assessment of G tube utilization.

- To assess the effect of celecoxib therapy on Quality of Life (QoL) compared to placebo.

Secondary Endpoint: completion of quality of life questionnaires EORTC QLQ-H&N43 and MDASI-HN as per the schedule of events.

- To assess the average number of treatment days missed during adjuvant radiation for patients on celecoxib compared to placebo.

Secondary Endpoint: the number of treatment days missed or delayed during adjuvant radiation.

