We recently demonstrated with the addition of celecoxib (a selective COX-2 inhibitor NSAID) in our immediate post-operative pain management pathway that we achieved a statistically significant and clinically meaningful decrease in the amount of opioids utilized while as an inpatient.⁸ The primary outcome of compliance will be analyzed by the average number of days from surgery to the initiation of radiation and adjuvant therapy. In our historical cohort of over 100 recent patients, the mean was 72.8 days (Standard Deviation 16.2 days). Our goal with this intervention is to reduce the days from surgery to radiation to 57.2 days or less because recent population-level data reaffirmed this milestone as significantly improving survival outcomes. Secondary outcomes are subjective pain scores, narcotic use, functional outcomes, and patient QOL and satisfaction with pain control throughout treatment, as well as the average number of days missed during adjuvant therapy. We will study these issues prospectively with monitoring progression through treatment, standardized pain questionnaires, pain score monitoring at each phase through treatment, patient satisfaction with pain, monitoring opioid use, and QOL and functional assessments. We strongly feel that

we can achieve a significant improvement in compliance with adjuvant radiation after surgery and will investigate this medication to achieve that end, which we hope will translate into improved disease-specific and overall survival for our cancer patients.

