⁷ Appendix 8: Treating Investigator Patient Assessment Guidance to be filled out by the treating investigator at the time of physical exam.

⁸ See Appendix 8: Treating Investigator Patient Assessment Guidance

⁹ Hematology to include CBC with platelets and differential.

¹⁰ Chemistry to include a complete metabolic panel (CMP).

¹¹ All women of child-bearing potential must have a negative pregnancy test 7 days prior to surgery.

¹² Only required if there is a known history of HIV, hepatitis B, or hepatitis C to confirm eligibility.

¹³ The radiation oncology consultation should be completed prior to registration if possible. This will include a discussion of the indications for adjuvant radiation treatment, a typical treatment course, and the anticipated/possible side effects so the subjects know what to expect if enrolled on trial.

¹⁴ Prior to surgery, the surgical team (physicians, nursing staff, pharmacy, etc.) will be notified about the patients involvement in the trial to ensure standard of care celecoxib and other prohibited therapies are not inadvertently administered.

¹⁵ Patients will complete 1 to 7 days of study therapy prior to surgery and continue twice daily dosing until the last radiation session.

¹⁶ Appendix 3: MDASI Head and Neck Cancer, Appendix 4: EORTC QLQ-H&N43, Appendix 5: Pain Satisfaction Questionnaire, and Appendix 7: Visual Analog Scale for Pain to be completed within 1 month of the scheduled time-points.

¹⁷ Appendix 6: Pre-treatment Questionnaire to be completed at the pre-operation visit.

¹⁸ Patients will be required to record all opioids taken for pain management on Appendix 4: Pain Management Diary while at home. Diary does not need to be maintained during admission post-surgery but should be started when study therapy is started and continue until completion of study therapy.

¹⁹ 5 weeks (\pm 7 days) post-operation the study team will contact the patient to review their medication diary, adverse events, and analgesic use record. If not returning to the study site at this time point, patients will be asked to fax or scan and email their Patient Dosing Diary and Pain Management Diary use records for the study team for review to ensure timely review of study drug compliance.

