11.4 Analgesic Use Record

All patients will be required to keep a diary of all opioids used for pain management during the trial. Patients should be instructed to record all opioid use from the start of study therapy to the end of study therapy. This information will be converted to Oral Morphine Equivalents (OME) and recorded in the eCRF.

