12.2.2 Pain Control and Management

Pain control and management will be compared between Arm 1 and Arm 2 and will be gauged through:

- Patient-reported subjective pain scores will be recorded on the visual analog scale of pain intensity averaged over a week at rest, with a swallow, and with a cough.
- Questionnaires focused on patient satisfaction with pain control.
- Narcotic consumption in daily total morphine equivalents averaged over a week collected from patient recorded opioid use throughout study therapy.

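### The opioid endpoint is said to cover all of study therapy, but the diary that feeds it is waived during the post-surgical admission and no other source is named for those days

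*Combined protocol and SAP*

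**What the plan says.** Section 1.2 lists the endpoint as "Narcotic consumption in daily total morphine equivalents averaged over a week". Section 12.2.2 adds the source and the period: "averaged over a week collected from patient recorded opioid use throughout study therapy". Section 11.4 tells patients to "record all opioid use from the start of study therapy to the end of study therapy", with no exception for time in hospital. It then has the diary converted to oral morphine equivalents (OME) and entered in the eCRF.

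Table 4, footnote 18 is narrower. It says "Patients will be required to record all opioids taken for pain management on Appendix 4: Pain Management Diary while at home", and then: "Diary does not need to be maintained during admission post-surgery". The same footnote starts the diary with study therapy and ends it with study therapy. Since therapy begins before surgery (Section 7.1), the admission falls inside that period.

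Section 13.4.2 assigns opioid use to a Gaussian mixed model that yields a mean difference and a 95% confidence interval. It does not say which week is averaged, or how inpatient days or missing diary days are handled.

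**The concern.** Reduced opioid use is one of the links in the trial's hypothesis (Section 2.1). The evidence offered for it is a "decrease in the amount of opioids utilized while as an inpatient" (Section 2.3), and Section 2.6 gives the size of the post-operative effect. A diary kept at home does not have to record anything in that setting.

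Two things are at stake. First, an effect concentrated in hospital could be missed by the endpoint. Second, the unrecorded span is the length of stay, which treatment could in principle change because the hypothesis is better pain control and recovery. If stay differs between arms, a home average taken close to discharge compares different days of recovery.

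**Working it through.** **1. Sources side by side**

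| Place | Period covered | Source for admission days |
|---|---|---|
| 11.4 | start to end of study therapy | patient diary, no exception |
| 12.2.2 | throughout study therapy | patient-recorded use |
| Table 4, footnote 18 | home only; waived during admission | none named |
| Table 4, concomitant medications | by visit | not linked to this endpoint |
| 15 | medical records verify CRF data | not linked to this endpoint |
| 13.4.2 | model only | no rule |

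Footnote 18 conflicts with 11.4 and 12.2.2, and nothing else fills the gap.

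**2. The plan's own opioid figure (Section 2.6)**

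Oral 9.9 + IV 3.9 = 13.8 mg per day, which agrees with the stated total of 14.

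Standard errors follow from the stated intervals (51 per group, t with 100 df, critical value about 1.984):
- Oral: (21.1 + 1.2)/2 ÷ 1.984 = 5.62. SD = 5.62/√(2/51) = 28.4. t = 1.77, p about 0.08.
- IV: (6.8 − 1.0)/2 ÷ 1.984 = 1.46. SD = 1.46/√(2/51) = 7.4. t = 2.67, p about 0.009.

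Only the IV component has an interval that excludes zero, and IV doses are what a home diary is least likely to capture.

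**3. Size of the gap**

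The documents give no length of stay. Assume L = 5 to 14 days from surgery, and 120 days for the approximately four months in the Study Summary.
- First post-operative week: min(L, 7) = 5 to 7 of 7 days unrecorded.
- Whole course: 5/120 = 4.2% to 14/120 = 11.7%. Over the six-month maximum (180 days) it is 2.8% to 7.8%.

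**4. What the endpoint would show (illustration)**

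Let the effect be 14 mg per day in hospital and h mg per day at home. The diary alone has expectation h. A full record averaged over 120 days has expectation (14L + h(120 − L))/120.

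| h | Diary alone | Full record, L = 5 | Full record, L = 14 |
|---|---|---|---|
| 0 | 0 | 0.58 | 1.63 |
| 7 | 7 | 7.29 | 7.82 |
| 14 | 14 | 14.0 | 14.0 |

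Averaged over the whole course, the gap moves the result little. It matters for the early post-operative period: with h = 0 the diary shows nothing, while an inpatient record would show 14 mg per day over the stay.

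**5. Precision**

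The total SD is 29.3 if oral and IV use are uncorrelated and 35.8 if perfectly correlated. With 20 per arm and two-sided 0.05 (normal approximation), power for 14 mg per day is 33% and 24% respectively, even with inpatient days recorded.

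**The case against.** The waiver relieves patients recovering from surgery of a diary; it does not exclude inpatient opioids from analysis. Concomitant medications and the analgesic record are both scheduled at the post-operation visit, and Section 2.6 shows that the site could recover post-operative opioid use per patient per day. Use before surgery, after discharge and during radiation is still covered. No objective is to replicate the inpatient finding, and the trial would have little power to do so. All of this stands. It shows that the data probably exist, which makes the repair cheap, but not that the plan uses them. Optional recording could also leave partial, self-selected inpatient data.

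A reader might infer more than the documents support:
- **That the highest-use days are lost.** This is plausible, but no section reports opioid use by period.
- **That all of post-operative week 1 is missing for every patient.** This needs a stay of at least 7 days. Table 4 allows the post-operation visit from day 5, and Section 10.2 has patients back in clinic 14 ± 7 days after surgery, so discharge within the first week is contemplated.
- **That the first weekly average uses whatever home days remain after discharge.** The averaging week is undefined. Appendices 5 and 7 ask about the past 7 days, so a week before each visit is at least as plausible.
- **That the comparison is biased against the arm discharged earlier.** This needs stay to differ by arm, early home days to carry higher doses, and the averaging window to sit next to discharge. The documents establish none of these.

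**Conclusion.** The point holds as a gap in data source and definition. Sections 11.4 and 12.2.2 promise coverage that footnote 18 withdraws for the admission, and no replacement source is named. Inpatient use, the setting of the site's only opioid effect estimate, is therefore absent or patchy, over a span fixed after randomisation.

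The size in days rests on the assumed 5 to 14 day stay and 120-day course in steps 3 and 4. Lack of comparability near discharge is conditional on stay differing by arm, and no direction or magnitude can be assigned to it.

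It should be corrected, in proportion: this is one measure under a secondary objective, with no sample size attached. The primary analysis and the sample size are unchanged.

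**What to change.** - Name the hospital medication administration record as the source of oral and IV opioid doses for admission days. Convert with the same OME table as the diary and enter the result in the eCRF. Patients need not keep a diary in hospital.
- Define the weekly averaging windows by days since surgery or by visit, using inpatient record plus home diary, and state how missing diary days are handled.
- Report inpatient and home periods separately as well as combined.
- Reconcile 11.4, 12.2.2 and footnote 18. In the same edit, correct the footnote's appendix number: it calls the pain diary Appendix 4, but the diary is Appendix 2.

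The cost is a wording change and chart abstraction of one existing admission record per patient, with no extra visit, procedure or patient burden.

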10 STUDY PROCEDURES

10.1 Screening

For screening procedures see the Schedule of Events and the Assessments Section. Screening activities may only begin after a subject has signed consent. All screening activities must take place within 28 days prior to surgery unless otherwise noted.

10.2 Treatment Period

Once a subject has completed screening, has been found to be eligible, and has been registered, treatment procedures may begin. At the pre-operation visit baseline, questionnaires will be completed and study medication will be dispensed. Patients will be instructed not to begin study medication until 6 days prior to the date of surgery to ensure 5 full days of twice-daily dosing. All pre-operation visit procedures must take place within 14 days prior to surgery unless otherwise noted.

Upon completion of 1 to 7 days of study therapy dosing, patients will undergo head and neck surgery as deemed appropriate by the treating investigator. 14 days (\pm 7 days) after surgery patients will return to the clinic and begin arrangements for adjuvant radiation therapy.

Five to thirty days post-operation every effort should be made to contact the patient to assess study drug compliance and adverse events. For patients not returning to the study site during this time frame, this contact may occur by phone or email. During this contact the study team will check the patient's Dosing Diary, Pain Management Diary, and adverse events. The patient will be asked to scan and email or fax their Dosing Diary and Pain Management Diary for assessment of adherence to the study regimen. However, if the patient does not have access to equipment to do this or is unwilling, failure to obtain the diaries will not be considered a deviation.

During adjuvant radiation, patients will return to clinic for evaluation (Mid-Radiation visit) 5 to 30 days after initiating radiation therapy. Patients will be instructed to continue study therapy twice-daily dosing until completion of their last radiation treatment.

See the Schedule of Events and the Assessments Section for treatment period procedures.

10.3 End of Treatment

Upon discontinuation of study treatment, an End of Treatment visit will occur. The end of treatment visit will occur 1 to 30 days after the last radiation treatment or after patient discontinues treatment. For End of Treatment procedures see the Schedule of Events and the Assessments Section.

11 STUDY ASSESSMENTS

Every effort should be made to ensure that the protocol-required tests and procedures are completed as described. However, it is anticipated that from time to time there may be circumstances, outside of the control of the Investigator that may make it unfeasible to perform the test. In these cases, the Investigator will take all steps necessary to ensure the safety and well-

being of the patient. When a protocol-required test cannot be performed, the Investigator will document the reason for this and any corrective and preventive actions that he or she has taken to ensure that normal processes are adhered to as soon as possible.

11.1 Physical Examinations and Vital Signs

Patients will have physical examinations to include major body systems, vital signs, assessment of Karnofsky performance status (see Appendix 8), Functional Oral Intake Score (Table 5), weight and height (height will be measured at screening only) at the time points described in the Schedule of Events. If necessary to facilitate scheduling, physical exam may occur one day prior to study treatment. Appendix 8: Treating Investigator Patient Assessment Guidance is to be filled out by the treating investigator at every physical exam.

Vital signs, to include blood pressure, pulse rate, and temperature will be also recorded at the time points described in the Schedule of Events.

Table 5: Functional Oral Intake Scale

| Score | Performance | Implication | Deficit |
|--------------|--------------------|---------------------------------|----------------|
| 1 | Aspirates saliva | Nothing by mouth | Profound |
| 2 | Tube dependent | Nothing by mouth/minimal trials | Profound |
| 3 | Tube dependent | Full trials by mouth | Severe |
| 4 | Total Oral | Single texture trials | Moderate |
| 5 | Total Oral | Multiple texture trials | Mild |
| 6 | Total Oral | By mouth/ restrictions | Minimal |
| 7 | Regular diet | By mouth/ no restrictions | Normal |

11.2 Adverse Events

Adverse events experienced during trial participation will be collected per the Schedule of Events and Adverse Events Section. Each study participant will be questioned about the occurrence of adverse events in a non-leading manner. Should the treating investigator feel that the adverse event is attributed to study therapy, then dose modification guidelines in the Dose Modification Section will be followed.

11.3 Laboratory Assessments

Samples for all laboratory assessments will be drawn at the time points indicated in the Schedule of Events and when clinically indicated. Laboratory tests may be performed up to 3 days prior to the scheduled clinic visit. All safety laboratory analyses will be performed by the local laboratory for each study center. All safety laboratory assessments must be reviewed

by the treating investigator. When applicable, results from the pregnancy test must also be available for review prior to dosing.

Table 6: Laboratory Assessments

| Laboratory Assessments | |
|---|--|
| CBC with Platelet Count and Differential | 
• White Blood Cell Count• Hemoglobin• Platelets• Absolute Neutrophil Count• Absolute Lymphocytes |
| Complete Metabolic Panel (Chemistry) | 
• Sodium• Potassium• Chloride• Carbon Dioxide• Alkaline Phosphatase• Aspartate Aminotransferase• Alanine Aminotransferase• Urea Nitrogen• Glucose• Creatinine• Calcium• Protein• Albumin• Bilirubin |
| Pregnancy | 
• Beta-hCG Qualitative Urine or Serum |

11.4 Analgesic Use Record

All patients will be required to keep a diary of all opioids used for pain management during the trial. Patients should be instructed to record all opioid use from the start of study therapy to the end of study therapy. This information will be converted to Oral Morphine Equivalents (OME) and recorded in the eCRF.

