5.1 Inclusion Criteria

Yes/No (Response of "no" = patient ineligible)

5.1.1 _____ Male or female subject aged ≥ 18 years.

5.1.2 _____ Advanced-stage (overall stage III and IV) head and neck cancers (sinonasal oral cavity, oropharynx, larynx, and hypopharynx) undergoing surgical resection and then adjuvant radiation. Primary and recurrence cases are acceptable.

5.1.3 _____ Karnofsky Performance Status of ≥ 70 .

5.1.4 _____ Adequate organ function demonstrated on labs drawn during the screening window and defined as:

- Hematologic:
 - Hemoglobin ≥ 10 g/dL
- Hepatic:
 - Total Bilirubin ≤ 2 mg/dL
 - AST(SGOT)/ALT(SGPT) $\leq 2.5 \times$ institutional ULN
 - Albumin > 3.5 g/dL
- Renal:
 - eGFR ≥ 30 mL/min/1.73m² or creatinine clearance ≥ 30 mL/min by Cockcroft-Gault:
 - Males:
$$\frac{(140 - \text{age}) \times \text{weight}[kg]}{\text{serum creatinine } \left[\frac{mg}{dL} \right] \times 72}$$
 - Females:
$$\left(\frac{(140 - \text{age}) \times \text{weight}[kg]}{\text{serum creatinine } \left[\frac{mg}{dL} \right] \times 72} \right) \times 0.85$$
 - Serum potassium within normal limits.

- 5.1.5** _____ Negative serum or urine pregnancy test at screening for women of childbearing potential.
- 5.1.6** _____ Highly effective contraception for female subjects throughout the study and for at least 5 days after the last dose of study therapy if the risk of conception exists (see [section 8.6](#)).
- 5.1.7** _____ Recovery to baseline or \leq Grade 1 CTCAE v5.0 from toxicities related to any prior treatments, unless AE(s) are clinically nonsignificant and/or stable on supportive therapy.
- 5.1.8** _____ Willing to maintain a diary of all opioids used during the trial for the treatment of pain.
- 5.1.9** _____ Able to provide informed consent and willing to sign an approved consent form that conforms to federal and institutional guidelines.
- 5.1.10** _____ Subject has verbally confirmed they are willing to complete adjuvant radiation therapy if recommended after surgery per protocol.
- 5.1.11** _____ Adjuvant radiation has been recommended by the institutional treatment planning conference with the best available data, but will be confirmed based on final surgical pathology.

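### The opioid diary stops with study drug, not with radiation, so the secondary opioid comparison can cover different treatment phases for different patients and be biased in either direction

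*Combined protocol and SAP*

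**What the plan says.** Three places tie opioid recording to study drug:

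- Section 11.4, second sentence: "Patients should be instructed to record all opioid use from the start of study therapy to the end of study therapy".
- Section 9, Table 4 footnote 18: the diary "should be started when study therapy is started and continue until completion of study therapy".
- Section 12.2.2, the endpoint itself: "Narcotic consumption in daily total morphine equivalents averaged over a week collected from patient recorded opioid use throughout study therapy".

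Two places describe a wider window:

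- Section 5.1.8: "Willing to maintain a diary of all opioids used during the trial for the treatment of pain".
- Section 11.4, first sentence: "All patients will be required to keep a diary of all opioids used for pain management during the trial".

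Patients who stay on drug are to "continue twice daily dosing until the last radiation session" (footnote 15), so for them both windows reach the end of radiation. Footnote 18 exempts everyone from the diary during the surgical stay: "Diary does not need to be maintained during admission post-surgery".

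Section 7.3.4 lists reasons for ending study drug early, including unacceptable toxicity, a hold of 14 days or more, more than 40% of doses missed, and refusal. Section 13.4.2 analyses opioid use with a Gaussian mixed model containing arm, provider and a patient effect nested in provider. It reports a mean difference and 95% confidence interval.

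**The concern.** The two windows agree only if nobody stops drug early. When someone does, the specific instruction and the endpoint definition both end recording, possibly with weeks of recovery and all of radiation still to come. The comparison becomes opioid use while still on the assigned product, over a stretch of treatment that differs between patients.

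Stopping may be related to arm and to pain: some patients may stop for toxicity, others because pain is not controlled. If the unrecorded weeks differ in opioid use from the recorded ones, and the pattern differs by arm, the estimated difference is biased. Radiation is the most exposed phase. Lower opioid use through to the end of adjuvant radiation is part of the hypothesis in 2.1, yet radiation-phase use would be seen only in patients still on drug. Unrecorded diary weeks cannot be reliably rebuilt afterwards.

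**Working it through.** **Figures in the plan.** No effect size, SD, power or early-stop rate is given for opioid use, so there is no figure for this endpoint to reproduce. The primary-endpoint power does reproduce (difference 72 - 57.2 = 14.8, SD 16.2, 20 per arm, two-sided t-test: 0.804 against the stated 80%), but nothing below rests on it.

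**Do early stoppers remain in the trial?** The off-study list in 7.3.5 does not name toxicity as such, dose holds or missed doses. Section 13.3.2 requires the lead-in, surgery and one radiation treatment for primary evaluability; it does not require staying on drug. Sections 12.1 and 12.2.3 collect the radiation start date and missed radiation days retrospectively. Such a patient's timing data are therefore kept while the later opioid diary is not.

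**How much record is lost?** Take the course as about 120 days (the Study Summary's approximate 4 months) and assume a stop on day 20 to 30. The patient then supplies 20/120 = 17% to 30/120 = 25% of the intended period. With radiation starting on average 72.8 days after surgery historically, or 57.2 days if the goal is met, a patient near those times who stops that early has no radiation-phase diary.

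**Does the model repair it?** Section 13.4.2 states no time term, analysis window or missing-data rule. Patients observed in different phases are compared directly. A likelihood fit would still assume that the missing weeks are missing at random given what was recorded.

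**Illustrative size.** In the weeks after stopping, let d be the share of an arm that has stopped and D the mean opioid use of stoppers minus that of continuers in the same weeks (1 = celecoxib, 0 = placebo). The full arm mean is the continuers' mean plus d x D, but only the continuers are recorded. Hence

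bias in (celecoxib - placebo) = -(d1 x D1 - d0 x D0).

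Inputs:

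- SD of opioid use, from the oral difference in 2.6 (95% CI -1.2 to 21.1, 51 per group): SE = 22.3/(2 x 1.984) = 5.62; SD = 5.62 x sqrt(51/2) = 28.4 mg/day.
- Stopping rates of 2% and 20%, borrowed from the toxicity-discontinuation scenarios in 12.3. Stops for other reasons would add to these.
- D from 0 to 1 SD, an assumption.

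| Case | d1, D1 | d0, D0 | Bias (mg/day) |
|---|---|---|---|
| a | 20%, 28.4 | 2%, 28.4 | -(5.68 - 0.57) = -5.1 |
| b | 2%, 28.4 | 20%, 28.4 | -(0.57 - 5.68) = +5.1 |
| c | 20%, 0 | 20%, 28.4 | -(0 - 5.68) = +5.7 |
| d | 20%, 0 | 20%, 14.2 | -(0 - 2.84) = +2.8 |
| e | 20%, 28.4 | 20%, 28.4 | 0 |

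Negative values favour celecoxib. The figures apply to the affected weeks; averaging in weeks before anyone stopped would dilute them.

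**Precision.** With SD 28.4, the 95% CI half-width is 2.024 x 28.4 x sqrt(2/20) = 18.2 mg/day at 20 per arm. At 16 per arm it is 2.042 x 28.4 x sqrt(2/16) = 20.5.

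**The case against.** **The text contradicts itself.** The first sentence of 11.4 and criterion 5.1.8 already cover the trial, and Table 4 lists the analgesic record and concomitant medications at the post-operation, mid-radiation and end-of-treatment visits. A reader might infer from the drug-based window that early stoppers have no opioid data at all. The documents do not support that: diary data before the stop are kept, and concomitant-medication entries may give partial information later. But 12.2.2 names the source of the endpoint as "collected from patient recorded opioid use throughout study therapy", so those entries do not replace the diary.

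**Follow-up may end anyway.** Section 10.3 lets discontinuation trigger the End of Treatment visit, and Table 4 has nothing after it, whereas footnote 6 times that visit only from the last radiation treatment. This stands: editing the three diary sentences alone would leave no scheduled point at which later diaries come in. Some reasons in 7.3.4, such as death, loss to follow-up or withdrawal of consent to procedures, cannot yield a diary under any wording.

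**An on-drug comparison may be intended,** since the objective in 1.2 speaks of patients on celecoxib. No section says so, 13.3 defines no on-drug population, and 2.1 extends the hypothesis to the end of radiation. An on-drug summary can be drawn from fuller data, but not the reverse.

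**Weight.** This is one secondary endpoint in a pilot, reported with an interval and no specified p-value. The illustrative bias is well inside the 18.2 mg/day half-width. That limits the importance of the point, but a wide interval does not correct a shift in the estimate.

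**Conclusion.** The point holds for the secondary opioid endpoint. As written, the operative instruction gives an on-drug comparison over unequal stretches of treatment and leaves it open to informative stopping. The two windows also conflict and need reconciling. The primary endpoint does not use the diary.

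Neither size nor direction can be known from the documents. The range of about -5 to +6 mg/day rests on assumed stopping rates and an assumed contrast of up to one SD. If stopping is unrelated to opioid need, or follows the same pattern in both arms, the difference is not biased.

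Two stronger readings are tempting and should not be drawn:

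- That the gap flatters whichever arm loses more patients. Direction depends on who stops as well as how many. If 20% of celecoxib patients stop with average use (D = 0) and 10% of placebo patients stop with use one SD higher, the bias is +0.10 x 28.4 = +2.8 mg/day, against celecoxib, although celecoxib lost more. Case c shows bias with equal stopping rates.
- That the bias can be expressed as a share of the 14 mg/day difference in 2.6. That figure is from a retrospective postoperative cohort, which 2.3 describes as inpatient use, while this diary is not required during the surgical admission. The SD used above has the same origin and serves only to set a scale.

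This is an inexpensive improvement that the sponsor should make.

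**What to change.** 1. In 11.4, footnote 18 and 12.2.2, have the diary continue to the last radiation treatment or, if no radiation is given, to a fixed time after surgery stated in the protocol. This should apply whether or not study drug is still being taken, to every patient who has not withdrawn from study procedures. It also removes the conflict with 5.1.8 and the first sentence of 11.4.
2. Align 10.3 and Table 4 (including footnote 6) so that an early stop does not end diary collection. Later diaries can come back by the email or fax route already described in 10.2 and footnote 19.
3. In 13.4.2, compare the randomised arms over the same defined weeks or treatment phases, using all recorded data regardless of drug status, and state how missing weeks are handled. An on-drug summary can be kept as a supplementary analysis.

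The cost is wording in several sections, some extra contact by the study team, and a longer diary for patients who stop early, some of whom may decline. Dosing, discontinuation criteria, eligibility and sample size are untouched. For patients who keep the diary, the bias term above becomes zero by design; for those who decline, an assumption about their missing weeks is still needed.
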